### Randomization and Blinding

Using a computer-generated random sequence, a person who was not involved in the experimental operation divided the patients into two groups in which FICB was achieved with either methylene blue and ropivacaine (MB+R group) or ropivacaine only (R group). All serial numbers were encoded sequentially, kept, and scheduled for each experiment by someone other than the researcher. Because methylene blue is a blue liquid, exposure to the color could expose the experimental group. Thus, blinding was achieved by having different researchers perform different steps in the study to avoid the color affecting the experiment. The steps of the experimental procedure,

including the extraction of the liquid medicine, performance of the nerve block, and postoperative follow-up, were performed by different anesthesiologists, who were only responsible for independent experimental procedures, did not know the information about the patient outside the experiment, and did not communicate with each other about the patient and the experiment. Catheterization was not performed for any patient to prevent the color of the urine from exposing the experimental group.

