#### **Operative Procedures**

Nerve Block

Before general anesthesia induction, FICB was performed under ultrasound guidance using the Edge II ultrasound device (Sonosite, USA). With the patient in supine position and the surgical area disinfected, the high-frequency ultrasound probe was placed perpendicular on the inguinal ligament. The probe was slowly moved until the "bowtie sign" created by the internal oblique and sartorius muscles was observed. This sign corresponds to the confluence of the fascia lata and fascia iliaca, which represents the fascia iliaca compartment. With an in-plane technique in the caudal to cranial direction, the needle tip was inserted deep to the fascia iliac. After confirming it could be withdrawn without blood, local anesthetic drugs in a volume of 30 ml were injected. Patients in the MB+R group received 0.25% ropivacaine (Product Batch Number: EE2344, Zhejiang Xianju Pharmaceutical Co., Ltd.) and 0.05% methylene blue (Product Batch Number: 2310032, Jichuan Pharmaceutical Group Co., Ltd.), and those in the R group received only 0.25% ropivacaine (same batch number).

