After successful nerve block, all patients were transferred to the operating room where they received routine monitoring of heart rate (HR), electrocardiogram (ECG), oxygen saturation (SpO2), etc. Radial artery puncture catheterization was performed under local anesthesia for invasive arterial pressure monitoring. For anesthesia induction, patients received an intravenous injection of propofol 1.0-2.0 mg/kg, rocuronium bromide 0.6 mg/kg, and sufentanil 0.2-0.3 µg/kg. The specifications of mechanical ventilation after endotracheal intubation were: tidal volume (VT) 6-8 ml/kg, respiratory rate (RR) 10–12 times/min, positive end expiratory pressure (PEEP) 3-5 cmH2O, and end-expiratory carbon dioxide partial pressure (PETCO2) 35~45 mmHg. Anesthesia was maintained by inhalation of 1.5%-2.0% sevoflurane along with intravenous infusion of remifentanil at 0.05-0.2 µg/kg/min and intermittent administration of rocuronium bromide 5-10 mg according to the intraoperative situation to maintain muscle relaxation. Blood pressure (BP) and HR fluctuation within 20% of baseline values was allowed according to the intraoperative situation. If BP dropped by >20% of the baseline value or if systolic BP was <90 mmHg, ephedrine 6 mg was given. If the HR was <50 beats/minute, an intravenous bolus of atropine 0.5 mg was given. All operations among included patients were performed by the same surgical team with the same surgical method, and the surgical method was hip replacement with posterolateral approach in the lateral decubitus position. The inhalation of sevoflurane and infusion of remifentanil was stopped 5 min before the end of the operation. After surgery, the patient was transferred to a recovery room, and

the endotracheal tube was removed once the patient was awake and spontaneous breathing had resumed. According to our pre-test experience, many patients refuse the use of analgesic pumps due to the relatively high cost, certain drug-related side effects, and the option of FICB. Thus, we did not include cases with post-surgical use of an analgesic pump in this study. In this study, fascia iliaca block was used to administer postoperative analgesia to patients. If the patients were not satisfied with the effect of fascia iliaca block, additional opioids were used for supplemental analgesia. At the same time, to avoid the effect of drugs on the level of patients' inflammatory factors, the use of non-steroidal analgesic drugs was prohibited.

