
### Study Outcomes

# Primary Outcomes

As a measure of pain, Visual Analog Scale (VAS) scores at both rest and with activity (passive straight leg raise at 45°) were recorded at the following time points: before block and at 2, 6, 12, 24, and 48 h postoperatively. The VAS score is a common way to assess pain using a sliding ruler about 10 cm long, marked with 10 scales on one side and "0" and "10" at each end. A score of 0 indicates no pain; a score of 10 indicates the most severe pain that is unbearable. The higher the score, the greater the degree of pain. In this study, a dedicated anesthesiologist assessed the pain of each included participant at different time points before and after surgery.

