# Secondary Outcomes

As indicators of inflammation, the values of hypersensitive C-reactive protein

(hs-CRP), procalcitonin (PCT), and the neutrophil-to-lymphocyte ratio (NLR) also were recorded on postoperative days 1 and 2.

HR and mean arterial pressure (MAP) values were recorded at the following time points: operating room entry (T1), immediately before skin incision (T2), 1 min after skin incision (T3), skin suture (T4), and 30 min after extubation (T5). The requirement of supplemental analgesia was noted within 48 h postoperatively, along with the number of times patients got out of bed to perform activities within 48 h postoperatively and the distance walked after the patient's first attempt to get out of bed. Any occurrence of adverse reactions such as nausea, vomiting, and arrhythmia within 48 h postoperatively also was recorded. Any drug-related nerve damage after surgery was noted. Nerve deficits were defined according to sensory findings: 0—no nerve damage, 1—minor sensory paresthesia, 2—complete sensory parasthesia, 3—complete motor defect with or without sensory paresthesia, and 4—complex regional pain syndrome. Two researchers who were blinded to the group allocation assessed these outcomes.

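### The colour precautions act on staff and the bedside; nothing described stops the patient, who supplies the VAS, from seeing the blue syringe or discoloured urine

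*Combined protocol and SAP*

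**What the plan says.** The section Randomization and Blinding recognises that the blue drug could give the arm away and describes two precautions.

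- **Separated roles.** Drug preparation, the block and postoperative follow-up "were performed by different anesthesiologists, who were only responsible for independent experimental procedures", and these anesthesiologists did not exchange information about the patient.
- **No urinary catheter.** "Catheterization was not performed for any patient to prevent the color of the urine from exposing the experimental group".

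On the treatment, Operative Procedures states: "Before general anesthesia induction, FICB was performed under ultrasound guidance", and "local anesthetic drugs in a volume of 30 ml were injected". Only the MB+R solution contains methylene blue, at 0.05%. No sedation for the block, and no screen, is mentioned.

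The primary outcome is VAS pain at rest and on passive leg raise, taken "before block and at 2, 6, 12, 24, and 48 h postoperatively". On who records it, Primary Outcomes says that "a dedicated anesthesiologist assessed the pain of each included participant at different time points before and after surgery".

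Rescue treatment depends on the patient: "If the patients were not satisfied with the effect of fascia iliaca block, additional opioids were used for supplemental analgesia". It is also an outcome under Secondary Outcomes: "The requirement of supplemental analgesia was noted within 48 h postoperatively". That section adds that two blinded researchers assessed its outcomes.

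**The concern.** The plan names the threat itself: colour can reveal the arm. Its precautions are directed at what staff know and at what hangs by the bed. An uncatheterised patient still passes urine and can look at it. Because the block precedes general anesthesia, the patient may also see a blue syringe. Methylene blue is given in one arm only, so either cue points to MB+R.

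This matters because of who rates pain. A 0 to 10 score of felt pain depends on the patient's report, even when an anesthesiologist holds the ruler. Rescue opioid follows the patient's dissatisfaction. If colour reaches the patient, it reaches the source of the primary outcome and of one important secondary outcome. The direction of any effect is open: belief in an added drug could lower scores, while alarm at discoloured urine could raise them. The section says that blinding was achieved without saying for whom, so the VAS could be read as masked at its source when the text supports only masking of assessors.

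**Working it through.** The plan gives no figure to reproduce on this point. The check sets each stated measure against the people it reaches, then counts the outcomes that depend on the patient.

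**Step 1. What each measure covers**

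| Measure | Where stated | Staff and assessors | Patient |
|---|---|---|---|
| Separate anesthesiologists, no communication between them | Randomization and Blinding | Covered | Not covered |
| No catheter | Randomization and Blinding | No drainage bag on view | Voided urine still visible |
| Two blinded researchers | Secondary Outcomes | Covered | Not covered |

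The available text describes no screen at the block, no concealed urine container, no colour-matched control and no statement that patients were masked.

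**Step 2. Dose**

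Inputs from the Nerve Block part of Operative Procedures: volume 30 ml; methylene blue 0.05%, which is 0.5 mg/ml.

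30 ml × 0.5 mg/ml = 15 mg per MB+R patient, and 0 mg in the R group.

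The documents do not say how often 15 mg by this route visibly colours urine. The point rests on the plan's own premise that it can.

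**Step 3. Timing**

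The pre-block VAS cannot be affected. All five postoperative ratings (2, 6, 12, 24 and 48 h) follow the block, so a patient who saw the syringe would carry that knowledge into each of them. The urine route is narrower: it needs a void before the rating, and no voiding times are given. Time out of bed within 48 h is itself an outcome, so patients are expected to be mobile in this window.

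**Step 4. Outcomes that depend on the patient**

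Counting one between-group comparison per outcome and time point:

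- VAS: 5 postoperative times × 2 conditions = 10
- Supplemental analgesia, times out of bed, distance walked: 1 + 1 + 1 = 3
- Total: 10 + 3 = 13

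Measured values that belief would hardly move:

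- hs-CRP, PCT and NLR: 3 markers × 2 days = 6
- HR and MAP: 2 measures × 5 time points = 10
- Total: 6 + 10 = 16

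Nausea and the sensory nerve grades rest partly on patient report and are in neither total. Thirteen is an upper bound on the comparisons that could be affected; it does not measure bias. No bias or error rate is computed, because the documents give no frequency of discolouration, no patient information and no sample size.

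**The case against.** The strongest reply is that the plan never promises patient blinding. It describes masking through staff roles and blinded researchers, and nowhere calls the trial double-blind. That stands: the text contains no false claim about patients. The gap is one of design, since following the plan exactly leaves the source of the primary outcome open to the cue the plan set out to hide.

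A second reply is that bias needs a chain of events: visible colour, a patient who notices it, and a patient who links it to an arm or is alarmed by it. The first link has no stated frequency, and the last depends on what patients were told. Consent pages are absent from the copy reviewed, which cannot be held against the plan. This also stands. A reader might infer that patients were in fact unmasked, or that the VAS results are biased in favour of methylene blue. The documents support neither inference.

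Third, the existing measures have value. A drainage bag shows urine continuously to anyone at the bedside, so omitting it removes a persistent exposure, and role separation keeps the follow-up assessor away from the syringe. Both are worth keeping. Neither changes what the patient can see.

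Finally, a patient may not have voided by 2 h, so not every VAS comparison need be exposed to urine colour. That is correct, and it is why 13 is only a ceiling.

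**Conclusion.** Patient masking of the VAS and of dissatisfaction-triggered rescue opioid is not secured by the measures described. At most 13 patient-dependent comparisons, including all 10 postoperative primary ones, could be affected; the 16 laboratory and haemodynamic comparisons are hardly exposed. Whether unmasking occurred, and the size and direction of any bias, cannot be determined from the documents.

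The conclusion assumes that the plan is right to treat colour as revealing, that a pain VAS depends on the patient's report although the plan says an anesthesiologist assessed it, and that no patient-directed measure exists in material removed from the copy reviewed. Confidence is medium for these reasons. The point is worth acting on, but it does not show that the results are invalid.

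**What to change.** Keep the no-catheter rule and the role separation. Add, identically in both arms:

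1. A drape between the patient's face and the syringe during the block.
2. Opaque lidded urinals or bedpans while patients are in bed.
3. A description of the trial as assessor-blinded, with VAS and supplemental analgesia interpreted on that basis.

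Do not tell patients to avoid mentioning urine, and do not hold their concerns back from assessors. Such an instruction draws attention to the cue and could lose adverse-reaction reports in the 48 h when they are being collected. Asking patients to guess their arm after the 48 h scores is optional and descriptive only: a guess can reflect pain relief itself, and asking does not secure masking.

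The cost is a drape, containers and slight extra ward work, with no extra patients and no change to eligibility. Containers do not help once patients walk to the toilet, so some exposure would remain. The document is written in the past tense; if conduct is complete, only item 3 applies, at no cost.

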#### **Operative Procedures**

Nerve Block

Before general anesthesia induction, FICB was performed under ultrasound guidance using the Edge II ultrasound device (Sonosite, USA). With the patient in supine position and the surgical area disinfected, the high-frequency ultrasound probe was placed perpendicular on the inguinal ligament. The probe was slowly moved until the "bowtie sign" created by the internal oblique and sartorius muscles was observed. This sign corresponds to the confluence of the fascia lata and fascia iliaca, which represents the fascia iliaca compartment. With an in-plane technique in the caudal to cranial direction, the needle tip was inserted deep to the fascia iliac. After confirming it could be withdrawn without blood, local anesthetic drugs in a volume of 30 ml were injected. Patients in the MB+R group received 0.25% ropivacaine (Product Batch Number: EE2344, Zhejiang Xianju Pharmaceutical Co., Ltd.) and 0.05% methylene blue (Product Batch Number: 2310032, Jichuan Pharmaceutical Group Co., Ltd.), and those in the R group received only 0.25% ropivacaine (same batch number).

After successful nerve block, all patients were transferred to the operating room where they received routine monitoring of heart rate (HR), electrocardiogram (ECG), oxygen saturation (SpO2), etc. Radial artery puncture catheterization was performed under local anesthesia for invasive arterial pressure monitoring. For anesthesia induction, patients received an intravenous injection of propofol 1.0-2.0 mg/kg, rocuronium bromide 0.6 mg/kg, and sufentanil 0.2-0.3 µg/kg. The specifications of mechanical ventilation after endotracheal intubation were: tidal volume (VT) 6-8 ml/kg, respiratory rate (RR) 10–12 times/min, positive end expiratory pressure (PEEP) 3-5 cmH2O, and end-expiratory carbon dioxide partial pressure (PETCO2) 35~45 mmHg. Anesthesia was maintained by inhalation of 1.5%-2.0% sevoflurane along with intravenous infusion of remifentanil at 0.05-0.2 µg/kg/min and intermittent administration of rocuronium bromide 5-10 mg according to the intraoperative situation to maintain muscle relaxation. Blood pressure (BP) and HR fluctuation within 20% of baseline values was allowed according to the intraoperative situation. If BP dropped by >20% of the baseline value or if systolic BP was <90 mmHg, ephedrine 6 mg was given. If the HR was <50 beats/minute, an intravenous bolus of atropine 0.5 mg was given. All operations among included patients were performed by the same surgical team with the same surgical method, and the surgical method was hip replacement with posterolateral approach in the lateral decubitus position. The inhalation of sevoflurane and infusion of remifentanil was stopped 5 min before the end of the operation. After surgery, the patient was transferred to a recovery room, and

the endotracheal tube was removed once the patient was awake and spontaneous breathing had resumed. According to our pre-test experience, many patients refuse the use of analgesic pumps due to the relatively high cost, certain drug-related side effects, and the option of FICB. Thus, we did not include cases with post-surgical use of an analgesic pump in this study. In this study, fascia iliaca block was used to administer postoperative analgesia to patients. If the patients were not satisfied with the effect of fascia iliaca block, additional opioids were used for supplemental analgesia. At the same time, to avoid the effect of drugs on the level of patients' inflammatory factors, the use of non-steroidal analgesic drugs was prohibited.

### Study Outcomes

# Primary Outcomes

As a measure of pain, Visual Analog Scale (VAS) scores at both rest and with activity (passive straight leg raise at 45°) were recorded at the following time points: before block and at 2, 6, 12, 24, and 48 h postoperatively. The VAS score is a common way to assess pain using a sliding ruler about 10 cm long, marked with 10 scales on one side and "0" and "10" at each end. A score of 0 indicates no pain; a score of 10 indicates the most severe pain that is unbearable. The higher the score, the greater the degree of pain. In this study, a dedicated anesthesiologist assessed the pain of each included participant at different time points before and after surgery.

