#### Statistical Methods

SPSS 25.0 software was used for statistical analysis. Normally distributed data were expressed as mean  $\pm$  SD, and group comparisons were performed using independent samples t-test. Data with a skewed distribution were expressed as median (M) and interquartile range (IQR), and non-parametric tests were used for comparisons. Friedman's test was used for intra-group comparisons. Count data were expressed as

number (%), and comparisons between groups were performed using the  $\chi^2$  test. P<0.05 was considered statistically significant.

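### The primary outcome holds ten postoperative pain comparisons, each open to testing at 5%, with no deciding comparison, success rule or multiplicity control

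*Combined protocol and SAP*

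**What the plan says.** Primary Outcomes, in the combined protocol and SAP, makes VAS pain the primary measure in two conditions, at rest and during a passive straight leg raise. The scores "were recorded at the following time points: before block and at 2, 6, 12, 24, and 48 h postoperatively". No time and no condition is ranked above another. Randomization and Blinding describes two arms, so each score gives one between-group contrast.

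Statistical Methods supplies the tests:

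- For normally distributed data, "group comparisons were performed using independent samples t-test".
- For skewed data, "non-parametric tests were used for comparisons", with the test left unnamed.
- Over time, "Friedman's test was used for intra-group comparisons".
- For significance, "P<0.05 was considered statistically significant".

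The document has no hierarchy, no any-or-all success rule, no multiplicity adjustment, and no summary measure or repeated-measures model that compares the arms across times. The natural reading is a separate between-group test at each time and condition, although the text does not say so outright.

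**The concern.** A primary outcome should lead to one pre-stated decision. This one can lead to many. A significant difference at 6 h on activity, at 24 h at rest, or at all times and in both conditions could each be presented as the primary result, and nothing in the plan rules any of them out.

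Friedman's test does not close the gap. It is assigned to comparisons within an arm, so it shows whether pain changes over time in that arm. It does not show whether adding methylene blue changes pain.

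The trial's main conclusion is at stake. With no rule fixed, the time, the condition or the criterion can be chosen once the results are known. A single significant time point then cannot be read as a confirmed primary effect.

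**Working it through.** **Inputs**

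| Input | Value | Source |
|---|---|---|
| Pain conditions | 2 (rest, activity) | Primary Outcomes |
| Postoperative times | 5 (2, 6, 12, 24, 48 h) | Primary Outcomes |
| Arms | 2, so one contrast per score | Randomization and Blinding |
| Threshold | 0.05 per comparison | Statistical Methods |
| Sidedness | two-sided | assumed; not stated |
| Correlation among the ten scores | 0 to 0.99 | assumed; not stated |

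The plan gives no familywise error rate, power or sample size, so there is no stated figure to reproduce.

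**Step 1. Count.** 2 × 5 = 10 postoperative comparisons. The pre-block scores are left out because they precede treatment.

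**Step 2. Any one significant, uncorrelated scores, no true effect.** 1 − (1 − 0.05)^10 = 1 − 0.5987 = 0.401.

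**Step 3. Any one significant, common correlation ρ.** With c = 1.960 and Φ, φ the standard normal distribution and density,

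P(any) = 1 − ∫ [Φ((c − √ρ·u)/√(1−ρ)) − Φ((−c − √ρ·u)/√(1−ρ))]^10 φ(u) du.

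| ρ | 0 | 0.3 | 0.5 | 0.7 | 0.8 | 0.9 | 0.95 | 0.99 |
|---|---|---|---|---|---|---|---|---|
| P(any) | 40.1% | 35.1% | 28.7% | 21.3% | 17.3% | 12.8% | 10.0% | 7.0% |

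**Step 4. A more realistic structure.** Here correlation decays over time (AR(1), adjacent-time value 0.4 to 0.9) and rest and activity correlate at 0.4 to 0.8. Simulated test statistics give 36% at the weakest correlations and 18% at the strongest.

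**Step 5. Check with actual tests.** Simulated trials with an assumed 30 patients per arm gave 39.6%, 29.1% and 12.9% with t-tests at ρ = 0, 0.5 and 0.9. Mann-Whitney tests on whole-number scores gave 29.0% at ρ = 0.5. The normal approximation is adequate.

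**Step 6. The opposite rule, all ten significant.** Replace the bracket in step 3 by one minus itself and integrate its tenth power. The result is 0.00014 at ρ = 0.5 and 0.011 at ρ = 0.9. It cannot exceed 5%, because it requires each single test to be significant.

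**Step 7. Holm over the ten.** If there is no true effect anywhere, a false positive requires the smallest P to fall below 0.05/10 = 0.005 (c = 2.807). The formula in step 3 gives 4.9%, 3.9% and 1.6% at ρ = 0, 0.5 and 0.9.

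**Step 8. Power cost at that first step.**

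- From 80% at 0.05: Φ(1.960 + 0.842 − 2.807) = Φ(−0.005) = 0.498.
- From 90% at 0.05: Φ(1.960 + 1.282 − 2.807) = Φ(0.435) = 0.668.

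**The case against.** The strongest reply is that the plan contains no rule under which any one significant result counts. What is documented is an absent rule, not an inflated error rate, and step 6 shows that an all-ten rule would be strict. That is right as far as it goes, and it is why the percentages are stated conditionally. It does not rescue the plan: the same data could be reported under either rule, and the error rate differs greatly between them.

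Three points about the figures also stand, as refinements:

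- The ends of the range are not bounds. Zero correlation among ten scores from one patient is implausible, and 13% is not a floor, since the rate falls towards 5% as the correlation nears 1. The structured range of 18–36% is more realistic, but it is also assumed.
- The figures count false results in both directions. A false result favouring the methylene blue arm has probability 1 − 0.975^10 = 22% with uncorrelated scores, about 14% at a correlation of 0.5 and about 6.4% at 0.9. These should be compared with a nominal 2.5%, so the inflation remains.
- Holm is conservative when scores are strongly correlated, and it needs valid P values. The plan does not name its non-parametric test.

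Finally, the document is written in the past tense. If the data have already been analysed, a rule added now is not prespecified and must be labelled accordingly. Because Holm covers the whole listed family, it leaves little room for selection.

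**Conclusion.** The concern holds and should be fixed before any primary claim is made. That the plan lacks a deciding comparison, a success rule and a multiplicity rule follows directly from its text. The size of the consequence is conditional. With two-sided tests, no true effect and any one significant result counted, the false-positive chance is about 13–40% for common correlations from 0.9 down to 0. It stayed above 5% at every correlation tried, up to 0.99. Applying the 0.05 threshold to each primary comparison as written does not hold the 5% level for the primary claim.

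**What to change.** Add to Statistical Methods that the ten postoperative between-group VAS comparisons form the primary family and are tested by Holm's procedure at a two-sided familywise level of 0.05. The smallest P is compared with 0.05/10 = 0.005, the next with 0.05/9 = 0.0056, and so on up to 0.05, stopping at the first failure. A primary effect is claimed only for comparisons that pass. Pre-block VAS is reported descriptively. The text should name the non-parametric test and state when the rule was adopted, including whether this was after outcome data by arm had been seen.

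One alternative is acceptable only if records show it was chosen before outcome data by arm were seen: a single named between-group comparison at two-sided 0.05, such as time-averaged VAS adjusted for the pre-block score, with individual times secondary. That would need a model the plan does not now contain.

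Holm needs no new data and no new model: a few sentences of text and adjusted P values from the existing tests. Its cost is power at a single time point. At the first step 80% falls to about 50%, and 90% to about 67%. These starting powers are illustrative, since the plan states none. They show the worst case, because later Holm steps are less strict.
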